### **2.5.3 Handling of missing values/censoring/discontinuations**

If a patient discontinued from the study prematurely missing data with respect to the target parameter were substituted by the last recorded value (last observation carried forward, LOCF). The LOCF method was only applied if a patient had at least one assessment after Baseline, i.e. on Visits Months 8 to 18. Otherwise, the patient was excluded from efficacy analysis within the FAS population. Prematurely performed month 18 visits were shifted to the closest visit following the date of last observation.

Patients of the FAS population who switched from the CNI group to the CNI-free group during the study or during follow-up, were analyzed in their randomized group.

Additionally, sensitivity analysis was performed with a repeated measurement analysis.

#### **2.5.4      Supportive analyses**

The primary analysis was once more performed with the PP set (as observed analysis, AOA)

The course of the GFR was of special interest. Changes from Baseline to each post-baseline measure were calculated by treatment group for each study visit.

In addition to quantitative analyses, the frequency distributions of patients with an improved GFR at study month 18 compared to BL (Month 6 post Tx) was compared between the two regimens. For group comparison, a Fisher's exact test was calculated.

Additionally to the analyses of data from the interval between BL (Month 6) and Month 18, the primary outcome variable was also evaluated for the interval between Screening (Month 3) and Baseline (Month 6).

In addition to the LOCF method described above, missing values were handled with an adapted LOCF method (LOCF-2), where the last recorded value under the initially given treatment after randomization was used for substitution of the missing data.

Results from these supportive analyses were interpreted in an explorative manner.

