10.8 Sample size calculation

The probable difference between the CNI-free - and the CNI-group in the GFR is estimated as $\delta = 8$ ml/min with $\sigma = 16$ ml/min. With $\alpha=.05$ (two sided significance level) and $1-\beta = 90\%$ (power), $n=86$ patients per group are required to demonstrate superior efficacy of the CNI-free regimen compared to the CNI-group in the GFR using the t-test [REDACTED]. To compensate for some uncertainty of the assumptions for sample size calculation, the calculated sample size is increased by $\approx 15\%$. Therefore, a total number of $N=200$ patients ($n=100$ per treatment group) will be randomized and treated in both treatment arms after Baseline (Month 6 post Tx).

In order to achieve the planned number of randomized patients as exactly as possible which may be hampered by the delay between inclusion (Screening – Month 3 post Tx) and randomization (Baseline - Month 6 post Tx), the rate of non-randomized patients will be determined when 150 patients will be randomized, and extrapolated to a number of 200 randomized patients. Recruitment will be stopped, when 200 patients + 120% of the extrapolated rate of non-randomized patients will be included at Screening. The further 20% of non-randomized patients are considered as a safety margin to avoid underrecruitment of randomized patients.

According to amendment 4, enrollment into this study will be terminated by 31st December 2015, by that time about 165 patients will have been recruited into this trial. Under the assumptions above, this would lead to a power of 82%. Since this sample size will contain also patients who discontinued the trial/medication early or who had other protocol deviations, the actual power will even be somewhat lower.

Under the assumptions specified in the initial protocol, the study will still have 82% power with the now reduced sample size. That means that the scientific value will not

be compromised with 82% probability. However, even if the study should just fail to reach statistical significance, it will most likely still show the presence (or absence) of a non-significant trend, which would contribute to the body of evidence for this treatment option.

11 Discussion and rationale for study design features

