### 1.1 Study design

This was a prospective, multi-center, randomized, controlled, parallel group, open label study in heart transplant recipients. Enrollment was terminated at 31st December 2015 with a protocol amendment. At that time 162 de novo heart transplant patients have been randomized to the two treatment groups at Baseline visit (Month 6 post Tx). The patients were recruited from 9 transplant centers in Germany.

During the first three months post Tx the patients may have been treated according to center standards. Latest after study inclusion (Month 3 post Tx ±2 weeks), the patients received an immunosuppressive regimen consisting of Cyclosporin A (based on C0-h level) or Tacrolimus (based on C0-h level) + Everolimus (target C0-h level: 5 – 10 ng/mL) or MPA + corticosteroids.

At Month 6 (±1 week) post transplantation (Baseline), patients whose eligibility was confirmed by additional in- and exclusion criteria were randomized and hence allocated to one of the two treatment groups in a 1:1 ratio in the following way:

A randomization list was produced under the responsibility of Novartis Biometrics Department using a validated system that automates the random assignment of treatment groups to randomization numbers in the specified 1:1 ratio (CNI group, CNI-free group). The randomization scheme was reviewed and locked after approval. According to the recommendations given in the ICH E9 Guideline “Statistical Principles for Clinical Trials” (CPMP, 1998), the used block length was specified in a separate document which was withheld from the study centers. The randomization list was kept sealed in a secure location.

At Baseline visit (Month 6 post Tx), all eligible patients were given a randomization number that assigns them to one of the treatment groups. The randomization numbers were sequentially allocated to the patients per center in the order of inclusion in the randomized treatment period.

Randomization of individual patients was performed centrally by a CRO. Allocation of a patient to one of the two treatment groups was performed in the following steps.

1. Information about patient enrollment (Screening Visit – Month 3 post Tx): Study sites informed the randomization department of the CRO about each patient inclusion via fax.

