### Death

- Source: Study completion CRF
- Occurrence: “Primary reason for premature discontinuation” = 10 (“Death”)
- Date of event: “Date of death”

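### A patient who dies after a rise in GFR can be counted as improved at Month 18, because last-value imputation does not exempt death

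*SAP*

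**What the plan says.** - **The analysis.** SAP section 2.5.4 compares "the frequency distributions of patients with an improved GFR at study month 18 compared to BL (Month 6 post Tx") between the two regimens with Fisher's exact test and labels the results exploratory. It gives no threshold for improvement, no denominator and no rule for patients who died. Protocol sections 10.5.4 and 10.6.4 plan the same comparison.
- **The missing-value rule.** SAP section 2.5.3 says that after premature discontinuation from the study "missing data with respect to the target parameter were substituted by the last recorded value". The only condition is one GFR from the Month 8 visit onward; patients without one are left out of the efficacy analysis. Protocol section 10.5.3 has the same rule.
- **The status of death.** SAP section 5.1.3 takes death from the study completion form, where it is one of the codes under "Primary reason for premature discontinuation". Neither document exempts it from carrying forward.
- **The second imputation.** SAP section 2.5.4 adds LOCF-2, which carries forward the last value obtained on the initially given randomised treatment. It does not mention death either.

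**The concern.** Taken together, these provisions let a patient whose GFR rose at Month 8, 9, 10 or 12, and who then died, enter the Month 18 table as improved. The table describes status at Month 18, and that patient has none.

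The route is not remote. Patients who stop only study treatment are still due a Month 18 assessment (Protocol sections 6.5.5, 6.5.6 and 7.1). Section 6.5.6 names death, withdrawal of consent and loss to follow-up as examples of why follow-up ends. Table 7-1 has no visit between Months 12 and 18, so a death in that half-year would normally be filled from a value at Month 12 or earlier.

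The effect need not be the same in both arms. Protocol section 10.5.3 expects GFR to stay stable or worsen on CNI and probably to improve without it. On that premise a death in the CNI-free arm is more likely to carry a raised last value. The same section argues that LOCF is conservative, but it considers neither death nor a yes/no outcome.

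The SAP would also classify one patient two ways: a failure in the treatment failure and MACE endpoints, and a renal improvement at Month 18.

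**Working it through.** **1. Inputs.** SAP section 1.1 reports 162 patients randomised and "allocated to one of the two treatment groups in a 1:1 ratio", so about N = 162/2 = 81 per arm. The exact split and the FAS sizes are not given. The documents also give no death counts, no improved share among survivors and no last values for patients who died; all of these are assumed below.

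The plan has no figure for this analysis to reproduce. Its sample size of 86 per group for the primary comparison (difference 8 mL/min, SD 16 mL/min, two-sided 0.05, 90% power) does reproduce with the noncentral t, but does not bear on deaths or responders.

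**2. Formulas.** For one arm, let d be the deaths before Month 18 with a post-baseline GFR, p the improved share among the others, and q the share of the d deaths whose last GFR was above the Month 6 value.

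- Last value carried forward: improved share = [(N − d)p + dq]/N
- Death counted as not improved: improved share = (N − d)p/N
- Excess in that arm: dq/N
- Shift in the difference, arm A minus arm B: (d_A q_A − d_B q_B)/N

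**3. One death.** 1/81 = 1.2 percentage points, if the last value was raised. A death whose last value was at or below baseline counts as not improved under either rule and adds nothing.

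**4. Illustration.** Arm A has 6 deaths, arm B has 2, q is equal in both arms, and p = 0.5. Fractional counts are expectations. With death as not improved, the difference A − B is (75 × 0.5 − 79 × 0.5)/81 = −2.47 points.

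| q | Shift = (6q − 2q)/81 | Difference A − B with LOCF |
|---|---|---|
| 0.2 | 0.8/81 = 0.99 points | −1.48 |
| 0.5 | 2.0/81 = 2.47 points | 0.00 |
| 0.8 | 3.2/81 = 3.95 points | +1.48 |

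Carrying forward therefore removes part or all of the penalty for the extra deaths. It gives arm A a net lead only when q exceeds p.

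**5. Reversal.** If 1 of 6 deaths in arm A and 3 of 3 in arm B had a raised last value, the shift is (1 − 3)/81 = −2.47 points, against the arm with more deaths.

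**6. Scale.** With a 50% improved share in each arm, the standard error of the difference is √(2 × 0.5 × 0.5/81) = 7.9 points.

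**The case against.** **LOCF is not named for this count.** SAP section 2.5.4 does not say which values it uses, and the same section contains an as-observed analysis of the PP set. This stands as a caveat. LOCF remains the likelier reading: it is the general rule for the target parameter, and section 2.5.4 introduces LOCF-2 as an addition to it. If LOCF was not meant, the count has no rule for missing values or death at all.

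**The analysis is exploratory and deaths are visible elsewhere.** They enter treatment failure and MACE, with Kaplan–Meier estimates and log-rank tests for each component, and each death has a narrative (SAP sections 2.6.2 and 2.7.2). This stands and limits the weight of the point. It does not correct the classification in the responder table.

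**The shift is small.** The largest value in the illustration, 3.95 points, is half a standard error. This also stands.

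**Scoring death as not improved is a choice.** It turns a renal count into a renal-plus-survival measure, and showing deaths beside the renal count is a defensible alternative. True, but it is the usual responder convention, and the present wording makes neither choice.

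**Stronger readings.** A reader might infer that the rule simply rewards the arm with more deaths. The documents do not support that: what matters is d × q in each arm, and step 5 shows a reversal. A reader might also take 2 to 6 deaths as overstating a responder rate by 2/81 = 2.5 to 6/81 = 7.4 points. That is a worst case for a single arm, with assumed counts and every last value raised; it is not the difference that Fisher's test compares. Nor does the rule reach every discontinuation: it needs study exit and a post-baseline GFR.

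**Conclusion.** The point holds in a limited form. Under the written rules, and on the likeliest reading of SAP section 2.5.4, a patient who dies after a GFR above the Month 6 value can be counted as improved at Month 18. Relative to counting death as not improved, this can favour the arm with more deaths whose last GFR was raised.

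The cost is 1.2 points per such death in an arm of 81, or about 1 to 4 points in the difference for 6 versus 2 deaths with q between 0.2 and 0.8. Those counts and shares are assumptions; neither direction nor size can be settled from the documents.

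The primary ANCOVA is not changed by this point. The same carried-forward values do enter its means, so their number should be shown there, but no effect on the primary result has been calculated and none should be inferred. The matter is worth correcting before the table is read on its own.

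**What to change.** In SAP section 2.5.4:

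- Define improved GFR at Month 18 as alive at Month 18 with a GFR above the Month 6 value.
- Count death before Month 18 as not improved, with all FAS patients of the arm in the denominator.
- State that LOCF applies to the other missing Month 18 values in this count, and that the rule for death also holds for any version using LOCF-2.
- Footnote the responder table and the primary table with the number of Month 18 values per arm that were carried forward past a death.

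The cost is a few lines of SAP text, one derived flag and two footnotes. Stated responder rates may be slightly lower, and the count must be described as a renal-plus-survival measure. Patients who die without any post-baseline GFR stay outside the FAS and so outside this table; the deaths reported under SAP section 2.7.2 should be read beside it.

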## 2 Statistical methods

### 2.1 Data analysis general information

All statistical analyses were performed [REDACTED]

[REDACTED] Analysis was carried out using the SAS (Statistial Analysis System) software, version 9.2, 2009, SAS Institute Inc., Cary, North Carolina, USA.

Analyses were done when all patients had completed the trial at 18 months post Tx (or discontinued prematurely).

The following periods were considered for analyses:

- The primary analysis of renal safety and tolerability concerns the **period of randomized treatment** between Month 6 (baseline) and Month 18 or the last assessment within this period in the event of a patient's premature discontinuation from the study. If indicated, e.g. for analysis of renal function and type and frequency of adverse events, the period from Month 6 to Month 18 was portioned into (a) the **switch period** between Month 6 and Month 9 and (b) the **maintenance period** between Months 9 and 18 after Tx.
- As a separate study period, the initial 3 months period between Screening and Baseline visit (**run-in period**) was analyzed with regard to treatment, efficacy, and safety of the immunosuppressive regimen.

In patients who discontinued prematurely from the study, the last available information under study treatmentwas analyzed.

Adverse events were analyzed separately for the initial 3 months period between Screening and Baseline visit (**Run-in period**) and for the randomized treatment period between Baseline visit (Month 6) and Month 18.

Significant events like rejection episodes, hemodynamic compromise, and MACE were additionally analyzed for the period between transplantation and Screening (Month 3 post Tx) (**Pre-screening period**).

Unless otherwise stated, all statistical tests were two-sided and used the 0.05 level of statistical significance. All summary statistics were presented by treatment group. Frequency distributions were provided for categorical variables. Descriptive statistics of mean, standard deviation, minimum, median and maximum were presented for continuous variables. Time to event data including rates of affected patients were assessed by Kaplan-Meier statistics and compared between the two groups with the logrank test.

Data from all centers that participated in this study were combined and the factor center was included in the analysis of the primary endpoint.

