### **2.5.2 Statistical hypothesis, model, and method of analysis**

The null hypothesis  $H_0$  of similar GFR level in both treatment groups

$$H_0: \mu_{\text{CNI-free}} = \mu_{\text{CNI-based}}$$

was tested against the two-sided alternative hypothesis of different efficacy (different GFR levels at month 18 after Tx) of the CNI-free regimen compared to the CNI-based regimen

$$H_1: \mu_{\text{CNI-free}} \neq \mu_{\text{CNI-based}}$$

with an analysis of covariance (ANCOVA) using “treatment” and “center” as factors and “baseline GFR value at Baseline visit 2 (Month 6)” as covariate. Type-I error probability was set to a two-sided  $\alpha=0.05$ . Adjusted means (=LS-means, LS: least square means) were presented for the treatment contrast of GFR at Month 18 post Tx together with its confidence interval and a two-sided p-value.

The FAS population was used for the primary analysis. This analysis followed the intention-to-treat principle and thus reflects the actual performance of the investigational drug under practical conditions (“pragmatic approach”).

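### The improved-GFR comparison at Month 18 uses a valid but inefficient unadjusted Fisher test, although improvement depends on the Month 6 GFR already used in the primary ANCOVA

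*SAP*

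**What the plan says.** SAP section 2.5.4 adds a responder comparison to the quantitative GFR analyses: the "frequency distributions of patients with an improved GFR at study month 18 compared to BL (Month 6 post Tx) was compared" between the regimens. It names the test, "For group comparison, a Fisher's exact test was calculated", and no covariate. The same section sets the status: "Results from these supportive analyses were interpreted in an explorative manner".

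The primary analysis of the same GFR data (SAP 2.5.2) is an ANCOVA with treatment and center as factors and "baseline GFR value at Baseline visit 2 (Month 6)” as covariate". SAP 2.6.2 evaluates serum creatinine and Cockcroft-Gault GFR in the same way as the primary measure.

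Protocol sections 10.5.4 and 10.6.4 plan the improved-GFR comparison without naming a test. For categorical variables in general, protocol 10.1 names the chi-square test, and the synopsis allows chi-square or Fisher. Neither document states a power for this comparison.

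**The concern.** *Improved* means that the Month 18 value exceeds the Month 6 value, so Month 6 GFR is part of the definition. Through regression to the mean, a patient with a low Month 6 value tends to rise and one with a high value tends to fall. A test that ignores Month 6 GFR leaves out a known predictor and does not correct for a chance baseline difference between the arms, as the ANCOVA does. Fisher's test is also conservative at this sample size.

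What is at stake is interpretation. A non-significant responder p-value beside a significant ANCOVA could be read as conflicting evidence on renal function when it only reflects a weaker test of the same data.

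**Working it through.** **Inputs from the documents.** The difference and SD are "estimated as $\delta = 8$ ml/min with $\sigma = 16$ ml/min" (protocol 10.8). SAP 2.1 says that "all statistical tests were two-sided and used the 0.05 level of statistical significance". SAP 1.1 reports 162 patients randomized 1:1.

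**Assumptions.** 81 per arm, all analysed; bivariate normal GFR at Months 6 and 18; mean change 0 in the CNI group; correlation r between the two visits, which the documents do not give. They also do not say whether sigma is the SD of the GFR level or of the change, so both readings are shown.

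**The plan's own figure.** By the normal approximation, n = 2 × 16² × (1.960 + 1.282)² / 8² = 84.1, or 85 per arm. The exact t-test gives 85.03, rounded up to the planned 86. It reproduces.

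**Dependence on baseline.** With equal SDs at both visits, corr(change, Month 6) = −√((1 − r)/2). This is −0.50 at r = 0.5 and −0.39 at r = 0.7.

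**Chance imbalance.** The standard error of the difference in baseline means is 16 × √(2/81) = 2.5 mL/min. With no treatment effect, an imbalance of one standard error shifts the responder difference by about 0.399 × (1 − r) × 2.5 / (16√(2(1 − r))). That is 3.1 percentage points at r = 0.5 and 2.4 at r = 0.7.

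**Expected proportions improved, sigma as SD of the level.** CNI group: 50%. CNI-free group: Φ(8 / (16√(2(1 − r)))), for example Φ(0.5) = 69.1% at r = 0.5.

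**Simulated power (%), sigma as SD of the level, difference 8.** There were 6,000 trials per row, and 2,500 for r = 0.3 and 0.9. Logistic means the likelihood-ratio test with Month 6 GFR. The ANCOVA has treatment and Month 6 GFR only, without center. The last two columns split the total gain; differences were taken before rounding.

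| r | Improved, CNI-free | Fisher | Chi-square | Logistic | ANCOVA | Total gain | From dropping Fisher | From baseline |
|---|---|---|---|---|---|---|---|---|
| 0.3 | 66.4 | 49.1 | 55.6 | 68.8 | 91.5 | 19.7 | 6.5 | 13.2 |
| 0.5 | 69.1 | 63.8 | 69.5 | 78.0 | 95.2 | 14.2 | 5.6 | 8.6 |
| 0.6 | 71.2 | 73.6 | 78.7 | 84.4 | 97.8 | 10.8 | 5.1 | 5.7 |
| 0.7 | 74.1 | 85.7 | 89.1 | 91.9 | 99.3 | 6.2 | 3.4 | 2.8 |
| 0.8 | 78.5 | 96.1 | 97.1 | 98.0 | 99.9 | 1.9 | 1.1 | 0.8 |
| 0.9 | 86.8 | 100 | 100 | 100 | 100 | 0 | 0 | 0 |

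The chi-square column agrees with the closed-form two-proportion power: 70.3% at r = 0.5 and 89.2% at r = 0.7. With a CNI mean change of −3 mL/min instead of 0, the total gains at r = 0.5 to 0.8 are 13.6, 10.6, 5.4 and 1.9.

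**Sigma as SD of the change, difference 8** (4,000 trials per row). The level SD is then 16/√(2(1 − r)).

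| r | Fisher | Chi-square | Logistic | ANCOVA | Total gain | From baseline |
|---|---|---|---|---|---|---|
| 0.5 | 63.9 | 69.9 | 78.0 | 95.4 | 14.1 | 8.1 |
| 0.6 | 64.9 | 70.1 | 76.5 | 93.9 | 11.6 | 6.5 |
| 0.7 | 65.3 | 70.7 | 75.0 | 92.9 | 9.7 | 4.3 |
| 0.8 | 64.4 | 70.0 | 73.3 | 91.5 | 8.9 | 3.2 |
| 0.9 | 64.5 | 70.2 | 72.8 | 90.0 | 8.3 | 2.7 |

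**Size under no effect** (r = 0.5 and 0.7, level reading). Fisher rejects in 3.1 to 3.9% of trials and chi-square in 4.6 to 5.3%. The adjusted test rejects in 4.6 to 5.6%, the range over several simulation runs.

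**Discordance with the ANCOVA** (level reading, 2,000 trials, difference 8). A significant ANCOVA beside a non-significant responder test occurs in 32% of trials with Fisher and 18% with the adjusted logistic test at r = 0.5. At r = 0.7 the figures are 13% and 7%.

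**The case against.** The strongest reply is that nothing here is an error. Under randomisation an unadjusted comparison of proportions is valid and controls type I error, and the protocol synopsis permits Fisher. The comparison is explorative, with no power target and no decision attached. The baseline-adjusted answer already exists in the primary ANCOVA, which is repeated in the per-protocol set and backed by a repeated-measures sensitivity analysis. All of this stands, and it limits the point to an improvement in efficiency.

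A second reply concerns the source of the gain. A reader might infer that leaving out baseline causes the whole loss. It does not: on the level reading, 5.6/14.2 = 39% of the gap at r = 0.5 and 3.4/6.2 = 55% at r = 0.7 comes from Fisher's conservatism, which an unadjusted, uncorrected chi-square test would recover. The adjusted test also runs at or slightly above the nominal level while Fisher runs well below it. The chi-square column, close to nominal size, is therefore the fair reference for the effect of baseline.

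A third reply is that dichotomising, not the choice of test, is the main reason why the responder result is weaker. That also stands: at r = 0.5 the adjusted test reaches 78%, against 95% for the ANCOVA.

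None of these replies shows a reason to leave out Month 6 GFR, beyond simplicity and an exact p-value.

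**Conclusion.** The point holds as a minor inefficiency. With sigma as the SD of the level, the adjusted test gains about 14 points of power at r = 0.5, 6 at 0.7, 2 at 0.8 and 0 at 0.9. Baseline adjustment itself accounts for about 3 to 9 of these points over r = 0.5 to 0.7. With sigma as the SD of the change, the total gain is about 8 to 14 points over r = 0.5 to 0.9. These figures rest on 81 per arm, normality, no mean change in the CNI group and a true difference of 8 mL/min.

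A reader might infer a general loss of 6 to 14 points. The documents do not support that as a fixed figure: on the level reading it needs a correlation of about 0.5 to 0.7, which they do not give. Nor do they support reading the Fisher test as biased, or the primary conclusion as at risk.

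**What to change.** In SAP 2.5.4, compare *improved* between the arms by logistic regression on treatment and Month 6 GFR, with a likelihood-ratio test. Report the baseline-standardised difference in proportions with its confidence interval, because the odds ratio is conditional on baseline and harder to read. Keep the raw frequencies as description, with the Fisher p-value if wanted. Record the change in SAP section 4, since the protocol names only chi-square or Fisher for categorical variables. Leave the explorative label as it is.

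The cost is a sentence of SAP text, one model and a short entry in section 4; no new data are needed. The downside is a model-based instead of an exact p-value, which matters little while roughly half to three quarters of patients are expected to improve. The change reduces discordance with the ANCOVA but does not remove it, because the ANCOVA does not dichotomise.
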